**Figure 2 Study Schema**

D1=Day 1; ITV=intravitreal; LPI=last patient in; M1=Month 1; M9=Month 9; PA=primary analysis; PRN=as needed (as per the refill criteria); RBZ PD=ranibizumab port delivery; RBZ=ranibizumab; SOC=standard of care; ✦ ranibizumab filled Implant inserted (Day 1).

Patients randomized to the Implant treatment arms will have the Implant (pre-filled with ranibizumab) surgically inserted in the study eye at their Day 1 visit, after which they will be evaluated monthly for the need for an Implant refill, based upon protocol-specified refill criteria (see Section 3.1.1), for the remainder of the study treatment duration (see Section 3.2). Patients randomized to the ITV injection treatment arm (control) will be treated monthly with ITV injections of ranibizumab, starting at their Day 1 visit and continuing for the remainder of the study treatment duration (see Section 3.2). The monthly ITV treatment arm patients will also be evaluated monthly according to the protocol-specified refill criteria (see Section 3.1.1), but will be treated monthly regardless of whether they meet the refill criteria. Study visits will be conducted every  $30 \pm 7$  days relative to the Day 1 visit.

Following implementation of Protocol GX28228, Version 5, if warranted, enrollment and implant insertion surgeries may be paused to enable real-time review of post-implant insertion safety data by the Internal Monitoring Committee (IMC). In the case of such a pause, dosing will continue as per the protocol for patients who have already received study drug (e.g., patients who have performed Day 1 visit), while patients who have not yet received study drug will stay in Pre-Screening, Run-In, Screening, or Randomization period (as applicable) and receive monthly open-label ITV ranibizumab treatment until enrollment and implant insertion surgeries are restarted. In addition, in the case of a pause, patients who have been randomized but have not yet received the study drug must repeat the Randomization assessments after enrollment and implant insertion surgeries have recommenced and before receiving the study drug. Patients who exceed nine total anti-VEGF doses before receiving the study drug will no longer be eligible for the study.

The study will include screening and randomization visits followed by a treatment period. Baseline measurements will be taken at the randomization visit. On the day of patient

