**Table 2 Dosing Guidelines Prior to Screening**

Historical anti-VEGF use in the study eye within the last 9 months prior to screening	Open-label ranibizumab dose(s) required prior to screening	Comments
Anti-VEGF treatment naive	2	The Sponsor will provide 2 ranibizumab doses prior to screening a
Single previous anti-VEGF dose	1	The Sponsor will provide 1 ranibizumab dose prior to screening a
2–8 prior anti-VEGF dose AND most recent dose was aflibercept or bevacizumab	1	The Sponsor will provide 1 ranibizumab dose prior to screening a
2–9 prior anti-VEGF dose AND most recent dose was ranibizumab	0	Patients can proceed directly to screening

VEGF = vascular endothelial growth factor.

a In the case of a pause of patient enrollment, additional ITV ranibizumab doses will be provided before receiving study drug, until enrollment and implant insertion surgeries recommence. Patients who exceed 9 total anti-VEGF doses before receiving the study drug will be excluded from the study.

A patient's screening visit should occur no sooner than 7 days following administration of the last ITV ranibizumab treatment in the study eye. All patients will be enrolled in the study on the day of their randomization visit and receive their Day 1 study treatment after conclusion of the Randomization visit. If necessary, the Day 1 study treatment may be scheduled at a later date.

Randomization visit cannot occur earlier than 28 days and no later than 37 days after the patient's last ITV ranibizumab treatment.

Day 1 study treatment visit cannot occur earlier than 28 days after and no later than 37 days after the patient's last ITV ranibizumab treatment, unless a patient randomized to the Implant arm needs more time to interrupt aspirin or NSAID usage 7 days before Day 1 (see Section 4.3.2.3). For these patients, Day 1 study treatment visit must occur no later than 45 days after the patient's last ITV ranibizumab treatment.

Patients who are randomized to the Implant treatment arms will have scheduled safety visit assessments on Day 2 ( $\pm 0$ ), Day 7 ( $\pm 2$  days), and Day 14 ( $\pm 2$  days) after their Day 1 visit. Starting at the Month 1 visit, the patients in the Implant treatment arms will be assessed monthly for the need for Implant refill with ranibizumab according to the

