### Schedule of Assessments for Implant Arms: Screening, Randomization, Day 1, Month 1 through Month 9, Month X, Safety Visits, and Final/Early Termination Visits (cont.)

Assessment	Screen a ≥7 days after RBZ tx	Rand b ≥28 and ≤37 days after RBZ tx	Day				Month									Month X Visit d	Safety Visit c	Final/ ET e	
			1 b	2 c	7 c	14 c	1	2	3	4	5	6	7	8	9				
Window (Days)				±0	±2	±2	±7	±7	±7	±7	±7	±7	±7	±7	±7	±7	±7	See footnote c	See footnote e
Eye fluid sample collection ao							Collect vitreous or aqueous humor sample at the start of explantation for patients undergoing an explantation procedure												

AMD=age-related macular degeneration; AREDS=Age-Related Eye Disease Study; BCVA=best corrected visual acuity; ET=end of treatment; IOP=intraocular pressure; ITV=intravitreal; IxRS=interactive Voice/Web response system; MacTSQ=Macular Degeneration Treatment Satisfaction Questionnaire; NA=not applicable; PK=pharmacokinetic; Rand=randomization; RBZ=ranibizumab; SA=safety visit; SD-OCT=spectral domain optical coherence tomography; tx=treatment.

Notes: All ocular assessments are to be performed for both eyes prior to study treatment unless noted otherwise. All assessments for a visit are to be performed on the same day, except those at screening.

a Screening cannot occur earlier than 7 days after the last standard-of-care of ITV ranibizumab treatment in the study eye.

b Patients randomized to Implant treatment arms will be scheduled at the conclusion of their randomization visit for their Implant insertion surgery (Day 1) on such a date that no less than 28 days and no more than 37 days have lapsed between the surgery and their the last standard-of-care ITV ranibizumab treatment in the study eye, unless a patient needs more time to interrupt aspirin or NSAID usage 7 days before Day 1 (see Section 4.3.2.3). For these patients, Day 1 study treatment visit must occur no later than 45 days after the patient's last ITV ranibizumab treatment. In the case of a pause of enrollment and implant insertion surgeries, patients who have been randomized but have not yet received the study drug must repeat all randomization assessments (except for the randomization transaction in IxRS) after enrollment and implant insertion surgeries recommence, before receiving the study drug.

## Appendix 1

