##### **4.4.2.1 Visual Acuity Change in Best Corrected Visual Acuity (BCVA)**

For change in BCVA from baseline, several supportive preliminary analyses will be performed as described below:

- Change from baseline in BCVA score averaged over Month 9 and Month 10 analyzed with an mixed effects repeated measures (MMRM) model
- Change from baseline in BCVA score averaged over Month 9 and Month 10 analyzed with a trimmed mean approach
- Change from baseline in BCVA score through Month 10 analyzed with an analysis of covariance (ANCOVA) model with missing data imputed by the last observation carry forward (LOCF) approach

- Change from baseline in BCVA score over time through Month 10 for patients treated after surgical Instruction for Use Version 10 (IFU v10) analyzed with descriptive statistics

The details for these analyses are provided as follows:

- Mixed effects with repeated measures (MMRM) analysis for change in BCVA score from baseline averaged over Month 9 and Month 10:

The change from baseline in BCVA score averaged over Month 9 and Month 10 will be compared between each PDS arm and the comparator intravitreal arm using a MMRM model. The model will include the change from baseline at Months 1 to 10 as the response variables and will include the categorical covariates of treatment group, visit, visit-by-treatment group interaction, the continuous baseline value for the response variable (in this case, baseline BCVA), as well as randomization stratification factors as fixed effects. Comparisons between each PDS and the intravitreal arm will be made using a composite contrast over Months 9 and 10. The MMRM model will assume an unstructured covariance structure. If there are convergence problems with the model, then a heterogeneous compound symmetry or a first order autoregressive (AR [1]) covariance structure may be fitted.

Best corrected visual acuity (BCVA) assessments will be censored after the time of rescue intravitreal anti-VEGF injection in the study eye and after the time of explant. Missing data will be implicitly imputed by the MMRM model, assuming a missing at random missing data mechanism (i.e., missing data are dependent on other observed variables but not on the missing data).

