When the proportion of the “must be trimmed” patients in either treatment group in the permuted data exceeds the planned trimmed fraction, the trimming fraction will be chosen adaptively as the greater of the proportions of the “must be trimmed” patients in the two treatment groups.

The percentage of patients to be trimmed will be based on an evaluation of percentage of patients meeting the trimming criteria by Month 9 rounded up to the nearest 5% to avoid many permutation tests from reverting to an adaptive approach. The analysis will be used to assess the difference in BCVA between two treatments excluding the true or assumed worst outcomes. Sensitivity analyses with different choices of trimming percentage may also be conducted.

- Change from baseline in BCVA score through Month 10 analyzed with an ANCOVA model:

The ANCOVA model will include the categorical covariates of treatment group, baseline BCVA score (continuous), and the randomization stratification factors as fixed effects. Separate models will be fit for each pairwise comparison and each study visit. Missing BCVA data, prior to or at Month 10 for each patient, will be imputed using the LOCF approach.

BCVA assessments will be censored after the time of rescue intravitreal anti-VEGF injection in the study eye and after the time of explant. These assessments after initiation of rescue treatment will be imputed using the LOCF approach.

- Descriptive summaries and figures will be provided for change from baseline in BCVA over time through Month 10 for patients treated after IFU Version 10. Observed data will be used. BCVA assessments will be censored after the time of rescue intravitreal anti-VEGF injection in the study eye and after the time of explant.

In addition, a descriptive summary for change from baseline in BCVA over time through the end of the study will be provided. This summary will include all observed data without censoring observations after use of rescue treatment or after explant.

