Adverse events (AEs) potentially related to the PDS Implant or Implant procedures will be summarized separately for two subgroups of patients based on the IFU version in use at the time of their randomization (before IFU 10 vs. IFU 10 forward). There was a study pause to evaluate post-implantation vitreous hemorrhage and modifications were made beginning with Version 10 with the aim to reduce the risk of vitreous hemorrhages.

Non-ocular AEs and SAEs will be tabulated using the following time windows relative to first ranibizumab injection or device implant following randomization:

- Cumulative rates through 10-month follow-up for each patient
- Cumulative rates for through the end of the study (expected Month 38)

A listing of patients who died during the study will be provided.

The number and percentage of patients with positive serum anti-drug antibodies (ADA) at baseline and post-baseline during the study period will be tabulated. Impact of positive serum ADA on efficacy and safety will be explored. A listing of patients with positive serum antibodies to ranibizumab will be provided.

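### The before/after IFU Version 10 safety split is anchored on randomization rather than Implant insertion, and the related BCVA summary uses a different, undefined anchor

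*SAP*

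**What the plan says.** SAP Section 4.6 plans separate summaries, in two patient subgroups, of the adverse events that may be related to the Implant or its procedures. The subgroups are formed "based on the IFU version in use at the time of their randomization (before IFU 10 vs. IFU 10 forward". The section gives the background: "There was a study pause to evaluate post-implantation vitreous hemorrhage and modifications were made beginning with Version 10", with the aim of reducing vitreous hemorrhage.

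SAP Section 4.4.2.1 also uses Version 10, but to select patients for a single summary. The list of analyses there includes change in BCVA through Month 10 "for patients treated after surgical Instruction for Use Version 10 (IFU v10) analyzed with descriptive statistics". The details repeat it as "change from baseline in BCVA over time through Month 10 for patients treated after IFU Version 10". Neither place says which date or which treatment decides who belongs.

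The protocol separates randomization from insertion. Section 3.1 says of patients who cannot be treated straight after the randomization visit: "If necessary, the Day 1 study treatment may be scheduled at a later date". It also provides for a pause: "Following implementation of Protocol GX28228, Version 5, if warranted, enrollment and implant insertion surgeries may be paused". In that case, "patients who have been randomized but have not yet received the study drug must repeat the Randomization assessments". Footnote b of Protocol Appendix 1, repeated in SAP Appendix 2, adds that these patients "must repeat all randomization assessments (except for the randomization transaction in IxRS) after enrollment and implant insertion surgeries recommence, before receiving the study drug".

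**The concern.** The safety split is there to show whether events after surgery differ between the earlier procedure and Version 10. For that purpose a patient belongs with the IFU under which the surgery was done. The stated rule uses the IFU in force when the patient was randomized, which can be an earlier version.

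The randomization anchor also stands apart within Section 4.6. The time windows for the same events run from first dose or implant surgery. The non-ocular windows run from first injection or device implant. The safety population is analyzed by the treatment actually received.

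At stake are the clarity of a before/after contrast in vitreous hemorrhage, and whether the Version 10 patients in the safety tables are the same people as the Version 10 patients in the BCVA summary.

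**Working it through.** The plan gives no figure to reproduce. The check sets the two rules side by side, bounds the gap between randomization and insertion, and works out the effect of misplacement.

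**1. Where each kind of patient falls.** Here the BCVA phrase is read as implanted once Version 10 was in use. That is an assumption, because the SAP does not define it.
- Randomized and implanted before Version 10: earlier group in 4.6, not in the BCVA subset.
- Randomized before Version 10, implanted under it: earlier group in 4.6, in the BCVA subset.
- Randomized and implanted under Version 10: later group in 4.6, in the BCVA subset.
- Randomized under Version 10, implanted under an earlier IFU: impossible unless a site reverted, since surgery follows randomization.

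Only the second kind is placed inconsistently, and always in the same direction.

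**2. Gap under ordinary scheduling.** Inputs from Protocol Section 3.1, in days after the last intravitreal ranibizumab injection: randomization no earlier than 28, Day 1 no later than 37, or no later than 45 for Implant patients who need time to stop aspirin or NSAIDs.
- Ordinary maximum gap: 37 − 28 = 9 days.
- With the exception: 45 − 28 = 17 days.

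Washout and operating-room availability (Protocol 4.1) and rescheduling for blood pressure (Protocol 4.3.2.3) have no separate window. Protocol 4.6.10.1 foresees a missed window, with a further injection possibly needed, and the bound does not apply then.

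**3. Gap under the pause rule.** Patients already randomized but not yet treated wait on monthly open-label injections, repeat the assessments after restart, and are not randomized again in IxRS. Their randomization date stays where it was while surgery moves past the restart, so the 9- and 17-day limits do not bind. Those who exceed nine anti-VEGF doses before study drug become ineligible, which limits how many can be carried over.

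**4. Effect of misplacement.** Let N be the number of patients in the earlier group and k the number of them implanted under Version 10. Let p0 be the event risk under the earlier procedure and p1 the risk under Version 10 onward.
- Expected rate in the earlier group = [(N − k)·p0 + k·p1] / N = p0 − (k/N)(p0 − p1).
- Expected rate in the later group = p1.
- Expected difference = (p0 − p1)(1 − k/N).

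The relative shrinkage is k/N, whatever the two risks are. With k = 0 nothing is lost. Neither N nor k is in the documents.

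**The case against.** The strongest defense is that randomization date is defined identically in all four arms. It keeps control and Implant patients randomized at the same time in the same era, and Section 4.6 reports rates for intravitreal as well as Implant patients. This stands as a small cost of changing the anchor. It does not outweigh exposure accuracy in a table about events tied to the Implant and its procedures.

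A second objection is that the IFU also covers filling, refill and explantation, so insertion date is not a complete description of exposure for all nine listed events. That is fair. The case for insertion rests on the pause having concerned hemorrhage after implantation and on the SAP calling the document surgical.

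A reader might also infer more than the documents support:
- That Version 10 is known to have changed the insertion procedure. Its text is not in the documents, so this is an inference.
- That Section 4.4.2.1 sets up a second, conflicting grouping. It defines one subset, by a loose phrase that could be shorthand for the same cohort.
- That patients were in fact misplaced, or that routine scheduling would misplace many. No pause date, Version 10 date or affected patient is given, and the ordinary gap is days. If enrollment stopped before Version 10 arrived, routine scheduling would contribute little.
- That the actual pause ran under the protocol's pause rule. The SAP does not say so.

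**Conclusion.** The point holds as a matter of definition. Section 4.6 uses an anchor that can put Version 10 surgeries in the earlier group, Section 4.4.2.1 leaves its own anchor unstated, and nothing reconciles them. Any error can only move patients into the earlier group. It understates a true reduction by the fraction k/N, provided that no site reverted to an earlier IFU, that misplaced patients carry the Version 10 risk, and that this risk is lower. The size cannot be determined from the documents and may be nil.

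The consequence is limited. The summaries are descriptive, the before/after contrast is not randomized, no test or decision rule uses it, and the time-to-first-refill analysis does not depend on it. It is worth considering because it is cheap to settle, not because a conclusion of the trial is in doubt.

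**What to change.** In SAP Section 4.6, define the subgroup by the IFU version in use on the date of Implant insertion, and by the first injection date for control patients if they are shown. Replace the undefined phrase in Section 4.4.2.1 with the same definition. Report how many patients change group compared with the randomization-date rule. If that count is zero, the question is closed.

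The cost is a phrase in each section and one count. The insertion date is already needed, because Section 4.4.1.1 measures time to first refill from the day of implantation, and the date Version 10 came into use is needed under the present rule too. The downside is that control and Implant patients randomized at the same time may fall in different eras, which a footnote to the tables should state.

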Patients in the ITV injection arm *will be evaluated monthly and will receive monthly study treatments (Day 1, Month 1 through Month X visit, see Appendix 2) until the Sponsor decides, based on the primary analysis results, to either terminate the study and discontinue study treatment, or offer patients entry into the RPDS Extension Study.* Their participation (excluding screening period) in the study will last approximately 13–38 months dependent on the date of their randomization to the study.

The patients in the Implant arms will be evaluated monthly for the Implant refill (see Appendix 1) until the Sponsor decides, based on the primary analysis results, to either terminate the study and discontinue study treatment, or offer patients entry into the RPDS *Extension Study*. If a patient requires refills outside of the protocol-defined visits window, the Medical Monitor must be contacted by the investigator. Study participation for patients in the Implant arms (excluding screening period) is expected to last approximately 13–38 months dependent on the date of their randomization to the study.

Study investigators will be qualified ophthalmologists, trained in the management of retinal diseases and ocular surgery and will be certified by a Sponsor-selected vendor to perform initial Implant fill, insertion, refill, and explantation. The surgical procedures involved in the use of the investigational devices are also detailed in the IFU document. It is strongly preferred that a site has one investigator who evaluates and treats all patients with a backup investigator selected. The site may opt to have two separate investigators but to maintain consistency in the evaluation and treatment of patients, it is strongly suggested that the same physician conduct the evaluation and treatment of a patient throughout the trial.

Study patients and all study site personnel will be masked to the Implant treatment arms' ranibizumab formulation assignment (10 mg/mL vs. 40 mg/mL vs. 100 mg/mL) until the study's conclusion (see Section 5.1.1.3 for more details on formulation assignment for

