### **4.6 SAFETY ANALYSES**

The safety analyses will use the safety population as described in Section 4.1 and 4.1.2. Missing data will not be imputed.

Adverse events (AEs) are coded using the current MedDRA version. Rates will be provided for intravitreal patients and PDS patients by dose arm and pooled across PDS arms.

For safety analyses, unless otherwise specified, AEs after the start of study treatment (intravitreal injection or Implant) will be included in the analyses; AEs from patients who are explanted will be included up to a follow-up period of 90 days after explant; the post-explant ocular AEs considered related to PDS will also be included in the analyses regardless of the timing of the AE onset. To fully characterize these patients' safety, a listing will be provided for ocular AEs that occurred  $\geq 90$  days after explant.

Frequency tables including patient incidence rates will be provided for the following:

- Ocular AEs and SAEs (study and fellow eye)
- Non-ocular AEs and SAEs (study and fellow eye)
- Adverse events of special interest (study and fellow eye)
  - AEs resulting from medication errors
  - An AE considered to be sight threatening
  - Suspected transmission of an infectious agent by the study drug
  - AEs resulting from use error or from intentional misuse of the PDS
  - ADEs, that is, AEs that are considered to be related to the PDS and to the use of the PDS
- Adverse events potentially related to the PDS Implant or Implant procedures:
  - Vitreous hemorrhage
  - Endophthalmitis
  - Retinal detachment
  - Conjunctival retraction
  - Conjunctival erosion
  - Conjunctival bleb
  - Conjunctival filtering bleb leak
  - Hyphema
  - Cataract

For AEs potentially related to the PDS Implant or Implant procedures in the study eye, incidence tables will be generated using the following time windows relative to first dose or implant surgery:

- $\leq 1$  month (up to the end of Month 1 visit window, 37 days)
- $> 1$  month
- during the entire study

In addition, ocular AEs and SAEs will be provided by causality as determined by the investigator.

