##### **Number of Patients**

Approximately 220 patients at up to 60 sites in the United States will be randomized in a 3:3:3:2 ratio to four treatment arms (60 per each of three Implant treatment arms and 40 to the ITV injection arm) within an approximate 24-month period of time.

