## **Appendix 1 Protocol Synopsis (cont.)**

Patients randomized to the Implant treatment arms will have the Implant (pre-filled with ranibizumab) surgically inserted in the study eye at their Day 1 visit, after which they will be evaluated monthly for the need for an Implant refill, based upon protocol-specified refill criteria, until the Sponsor decides, based on the primary analysis results, to either terminate the study and discontinue study treatment, or offer patients entry into the RPDS *Extension Study*. The duration of their participation in the study is expected to last approximately 13–38 months dependent on the date of their randomization to the study.

Patients randomized to the ITV injection treatment arm (control) will be treated monthly with ITV injections of ranibizumab *until the Sponsor decides, based on the primary analysis results, to either terminate the study and discontinue study treatment, or offer patients entry into the RPDS Extension Study*. The duration of their participation in the study is expected to last approximately 13–38 months dependent on the date of their randomization to the study.

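### SAP 4.6 labels a cumulative AE rate 'Month 38' although planned follow-up is about 13–38 months, and it names no safety estimate that allows for unequal follow-up

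*SAP*

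**What the plan says.** SAP 4.6 sets the time origin at each patient's first treatment: "Non-ocular AEs and SAEs will be tabulated using the following time windows relative to first ranibizumab injection or device implant following randomization". Two windows follow. The first is "Cumulative rates through 10-month follow-up for each patient". The second is "Cumulative rates for through the end of the study (expected Month 38", given in parentheses as the expected end of study.

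The only stated form for AE results is in the same section: "Frequency tables including patient incidence rates will be provided for the following". Missing safety data are not imputed. No Kaplan-Meier, cumulative-incidence or person-time AE estimate is named, and no numbers at risk. SAP 4.6.1 summarizes exposure to ranibizumab but does not link it to AE counts.

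Implant-related study-eye AEs are tabulated up to 1 month, after 1 month, and over the whole study. They are also summarized by the IFU version in force when the patient was randomized (before Version 10, or Version 10 onward). AEs of explanted patients count for 90 days after explant, except that PDS-related ocular AEs count without a time limit.

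On follow-up, SAP Appendix 1 says patients are randomized "within an approximate 24-month period of time" and that participation is "expected to last approximately 13–38 months dependent on the date of their randomization". Protocol 3.1 gives the same 13–38 months for the Implant arms and the ITV arm.

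**The concern.** A window counted from first treatment and labelled Month 38 looks like a 38-month patient-time rate. Under the planned accrual, only the earliest patients could supply 38 months. In a simple table of patients with an event over patients treated, someone followed for 13 months without an event counts the same as someone followed for 38.

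Two things are at stake. The first is the absolute long-term figure for non-ocular AEs and SAEs, which a reader could take as a 38-month risk. The second is any contrast between groups with different follow-up. The IFU split is by randomization date, so the earlier group has been watched longer, and events after the first month could look less frequent under Version 10 with no change in risk.

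**Working it through.** **Inputs from the documents.** Accrual about 24 months (Protocol 3.1, SAP Appendix 1). Primary data about 4 months after the last patient's Month 9 visit (Protocol 3.2). Study length about 38 months (Protocol 3.2), which Protocol Appendix 21, 6.3.5 says includes enrolment. Participation 13–38 months in both arm types.

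**Not in the documents, so assumed and varied.** Accrual shape (a study pause occurred), AE frequency, AE hazard shape, dropout over the safety period, and the date of the IFU change.

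**1. Reproduce the plan's range.** Last patient: 9 + 4 = 13 months. First patient: 24 + 9 + 4 = 37 months, or about 38 with a final visit a month later. The plan's 13–38 months reproduces. Thirty-eight is a calendar length that only the first patients reach as follow-up.

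**2. Who reaches each month.** With follow-up uniform on 13–38, the share reaching month m is (38 − m)/25: 20/25 = 80% at Month 18, 14/25 = 56% at Month 24, and 2/25 = 8% at Month 36. Everyone is planned to pass Month 10. Mean follow-up is (13 + 38)/2 = 25.5 months, and 25.5/38 = 67.1% of the window.

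**3. Size of the gap if the crude figure is read as 38-month risk.** Let F be the true 38-month risk and λ = −ln(1 − F)/38. The crude proportion is C = 1 − [exp(−13λ) − exp(−38λ)]/(25λ), and the understatement is 1 − C/F. For F = 10%: λ = 0.10536/38 = 0.002773, and C = 1 − (0.9646 − 0.9000)/0.0693 = 6.8%.

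| True 38-month risk | Crude | Understatement |
|---|---|---|
| Very rare | – | 32.9% |
| 10% | 6.8% | 31.9% |
| 30% | 21.1% | 29.6% |
| 45% | 32.7% | 27.5% |
| 80% | 64.4% | 19.5% |
| 99% | 93.5% | 5.6% |

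Other assumptions:

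- Early-onset hazard (Weibull shape 0.5): 18.9% for rare events, 4.6% at 95% risk.
- Rising hazard (shape 1.3): 39.5% for rare events.
- Back-loaded triangular accrual: mean follow-up 21.3 months, 43.8% for rare events. Front-loaded: 29.7 months, 21.9%.
- Dropout of 8% per 9 months: mean 22.5 months, 40.7% for rare events. Dropout of 8% in total by Month 38: 24.7 months, 34.9%. The 8% comes from the clogging analysis (Protocol Appendix 21, 7.4), so it is only indicative.

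The range is about 5% to 44%. Combining extremes can go outside it: 99% risk with shape 0.5 gives 1.8%.

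**4. IFU subgroups.** Take the same true 38-month risk of 10% in both groups, constant hazard, uniform accrual and a split at mid-accrual. The earlier group then has 25.5–38 months of follow-up and the later group 13–25.5 months. With 12.5λ = 0.03466:

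- Before: 1 − (0.9317 − 0.9000)/0.03466 = 8.4%.
- From Version 10: 1 − (0.9646 − 0.9317)/0.03466 = 5.2%.

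That is an apparent reduction of about 38% with no change in risk (36% with the split at one third of accrual, 41% at two thirds). The first-month window is essentially untouched, because planned follow-up is at least 13 months.

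**5. Randomized arms.** Planned follow-up is the same in all arms, so staggered entry alone does not distort the comparison. Counted time can still differ. The 90-day post-explant cut applies to PDS patients, and no matching cut is stated for ITV patients who stop treatment, who are asked to keep attending monthly visits until the last patient's Month 9 visit (Protocol 3.1).

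**The case against.** The strongest reply is that the second window is a study milestone. The words 'for each patient' belong only to the 10-month bullet, and Month 38 can be read as the expected calendar end of study. On that reading, patients with an event over patients treated is a valid incidence over variable follow-up, and nothing is biased. This stands, and it leaves a label problem: the windows are declared to run from first treatment, so Month 38 invites the other reading.

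A reader might also infer that the plan understates AE rates in general by about 30%. The documents do not support that. The Month 38 window covers non-ocular AEs and SAEs only; the implant-related ocular windows make no 38-month claim. The SAP says cumulative rates without naming an estimator, so the crude proportion is inferred from its patient incidence tables. The 30% also needs an accrual curve, hazard shape and event frequency that the documents do not give.

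Nor do the documents support a general bias between PDS and ITV, since planned follow-up is common to all arms. The 10-month window already gives a nearly common-duration rate, and the study is exploratory. Incidence tables are acceptable as description. They do not, however, correct for follow-up where groups differ in it, as the IFU groups do by construction. The SAP does not say that the IFU summaries will use the later windows, but it does not confine them to the first month either.

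**Conclusion.** The point holds in a limited form. The Month 38 label does not fit a window timed from first treatment when planned follow-up is about 13–38 months, and SAP 4.6 gives no AE estimate that allows for unequal follow-up. If the figure is read as a 38-month risk, the understatement is about 27–33% under uniform accrual, constant hazard, no dropout and a true risk up to about 45%, and about 5–44% across the other cases. If it is read as incidence to study end, only the label misleads.

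The more consequential exposure is the IFU comparison outside the first month, where equal risks could appear as about 8.4% and 5.2% in the illustration; the actual size depends on when Version 10 took effect. Between randomized arms, the effect comes mainly through the post-explant cut or differential discontinuation. This is a worthwhile improvement to the safety reporting and does not touch the primary efficacy analysis.

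**What to change.** Keep the planned counts and percentages, and make three changes to SAP 4.6:

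- Relabel the second non-ocular window as 'through end of study (follow-up about 13–38 months)'.
- For the end-of-study, after-1-month and whole-study windows, add events per 100 patient-years by arm, for pooled PDS and by IFU subgroup. Patient-years should follow the same counting rules as the events, including the 90-day post-explant cut.
- Where a cumulative rate is quoted, give the Kaplan-Meier or cumulative-incidence estimate at times the follow-up supports (for example Months 10, 18 and 24), with numbers at risk.

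The cost is SAP wording and one extra set of safety tables from onset and treatment dates already collected. The SAP already plans censoring and Kaplan-Meier methods for refill times (4.4.1.1 and 4.4.1.2).
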